# 8.3. Treatment Compliance

Deramiocel will be administered in a licensed infusion center, or other appropriate unit according to a site's institutional standards, by appropriately trained medical personnel who will document the actual volume administered at each infusion.

Deramiocel administration occurs every 3 months anchored from the previous infusion for a total of up to 20 infusions (Day 1, Month 3, Month 6, Month 9, Month 12, Month 15, Month 18, Month 21, Month 24, Month 27, Month 30, Month 33, Month 36, Month 39, Month 42, Month 45, Month 48, Month 51, Month 54, and Month 57). Should a subject's infusion schedule need to be altered, please contact the Medical Monitor to discuss the subject-specific case and out-of-window administration of deramiocel.
## 9. INVESTIGATIONAL PRODUCT MATERIALS AND MANAGEMENT

Detailed investigational product information can be found in the Investigator's Brochure (IB) and the Investigational Product Manual. Below and elsewhere in the protocol, reference is made to an investigational pharmacist which is typically a person licensed to dispense prescription medication usually within a special unit of the institutional pharmacy that handles all investigational products. Deramiocel is a cell-based investigational product, therefore the chain of custody and responsibility for preparation of the investigational product may reside within another institutional department or unit within institution or an outside laboratory designated for such purposes by institution, such as a center for cellular therapy or human cellular therapy laboratory or similar name, in which case "investigational pharmacy" shall mean the special center, laboratory or unit within or outside the institution designated to handle all cell-based therapies and "investigational pharmacist or other designee" shall mean the person delegated by the Principal Investigator as having the role in receiving, storing and preparing deramiocel who may not be a licensed pharmacist.

Page 38 of 78 Capricor, Inc. - Company Confidential

Page 40 of 78 Capricor, Inc. - Company Confidential

## 9.6. Discontinuation of Medications Prior to Infusion

If clinically acceptable in the judgement of the Investigator, beta blockers and angiotensinconverting enzyme inhibitors (ACEi) should not be administered on the day of infusion. Furthermore, since all subjects who are pre-treated with glucocorticoids, as determined by the Investigator as part of their pre-medications, will likely start pre-treatment with glucocorticoids beginning 12 - 14 hours prior to infusion (see Section 9.7), their standing steroid medications schedule may need to be adjusted. Specifically, standing glucocorticoids should not be administered in the setting of glucocorticoid pre-treatment within 24 hours prior to the time of scheduled infusion or on the day of the deramiocel infusion.

## 9.7. Pre-Infusion Guidance for Minimizing Risk of Potential Severe Hypersensitivity Reaction

As discussed in Section 8.2, Capricor requires treatment of all subjects prior to each deramiocel infusion to minimize the risk of a potential severe allergic reaction. It is strongly encouraged that pre-medication be administered according to the guidelines described in this section, including the administration of high-dose oral steroids, H1 and H2 blockers; however, investigative sites may use institutional protocols established for anaphylaxis prevention should they be at least physiologically comparable to the guidelines below.

Final decisions regarding the medication(s), dose(s) administered, and route(s) of administration are to be determined by the Investigator taking into consideration the subject's medical history. For any pre-treatment medication administered, the FDA approved label should be reviewed for information on potential side effects and/or drug interactions and followed for detailed instructions on weight-based dosing.

Please see Section 9.6 for recommendations on holding beta blockers, ACEi and standing steroid doses within 24 hours of scheduled infusion.

### 9.8. Administration

Deramiocel will be administered in an outpatient setting at the investigative site on Day 1 and Months 3, 6, 9, 12, 15, 18, 21, 24, 27, 30, 33, 36, 39, 42, 45, 48, 51, 54, and 57. Subjects must complete all trial safety assessments prior to the deramiocel infusion, excluding those related to the deramiocel infusion (e.g., post-infusion monitoring). CAP-1002 will be administered as an IV infusion using a commercially available syringe pump approved for human use at infusion rates of 1 mL/min to 3 mL/min.

to each infusion, it is recommended that site personnel meet to discuss the logistics for that specific infusion.

Capricor requires that subjects be treated prior to each deramiocel infusion with medications that minimize the risk of potential severe allergic reactions (see Section 9.7).

Page 43 of 78 Capricor, Inc. - Company Confidential

## 9.9. Post-Infusion Monitoring

Subjects will remain in the outpatient setting for at least 2 hours post infusion for observation, or longer should that be warranted in the judgement of the treating clinician. Investigative sites will observe their local institutional policies for post parenteral infusion monitoring. The subject's pulse oximetry (SpO2) will be monitored for at least 30 minutes post infusion. A site Investigator will assess the subject for adverse events and approve his discharge the same day if medically cleared.

If clinically indicated, an unscheduled in-person visit will be performed at the investigative site with targeted assessments based on presentation of signs and symptoms of the subject following infusion.

## 9.10. Accountability

Good Clinical Practice (GCP) and FDA regulations assign responsibility for investigational product accountability at the trial site with the Principal Investigator. The Investigator may elect to delegate this responsibility to the investigational pharmacist, or other designee, who is under the supervision of the Investigator.

The responsible person must maintain a record of deramiocel received, prepared, administered and returned/destroyed. Therefore, deramiocel accountability must be maintained throughout the trial to show clear product traceability at all times. Details regarding deramiocel accountability will include dates, quantities, batch/serial numbers, expiration dates if applicable, storage conditions and the unique code assigned to the deramiocel and subjects. Deramiocel accountability must adequately document that the subjects were provided the correct vial and reconcile all deramiocel received from Capricor's drug depot. Further information on deramiocel accountability is found in the Investigational Product Manual.

## 9.11. Handling and Disposal

All deramiocel materials will be disposed following each infusion. Site personnel will follow institutional policies on the proper disposal of containers and disposables coming into contact with the deramiocel. Generally, disposal like other biohazard red-bag trash that is ultimately

Page 44 of 78 Capricor, Inc. - Company Confidential incinerated should be sufficient to meet local institutional policies and any other regulations or laws.

#### 10. ASSESSMENT OF SAFETY

Assessments to evaluate safety will be performed at trial visits as indicated in Appendix B.

#### 10.1. Safety Assessments

#### 10.1.1. Vital Signs

Heart rate, systolic and diastolic blood pressure, respiratory rate, body temperature, and blood oxygen saturation (SpO2) will be measured after the subject has rested for approximately 5 minutes. A single set of values will be captured.

A subject's SpO2 will be monitored for at least 30 minutes following each deramiocel infusion (see Section 9.9).

Vital signs will be performed using equipment provided by investigative sites that has been properly calibrated per institutional guidelines.

#### 10.1.2. Weight and Height

Weight and ulna length measurement for calculation of height will be performed.

Investigative sites will make every effort to perform a weight measurement without the subject's wheelchair or other assistive device (e.g., walker), if applicable.

Height will be calculated using the subject's ulna length (Gauld et al., 2004) for all subjects. It is critical to reduce variability in ulna length measurements across investigative sites. Therefore, site personnel must complete trial-specific training prior to measuring a subject's ulna length.

#### Table 4:Height Calculation from Ulna Length

Height (cm) = [4.605 x Ulna Length (cm)] + [1.308 x Age (years)] + 28.003

Centimeter and year entries must include decimal places to the tenth place. If a subject is 18 years or older, enter "18" in the formula for age.

#### 10.1.3. Physical Examination

The physical exam (PE) is not considered a standard of care assessment as the examiner will be assessing for research events. Therefore, the physical exam is to be conducted only by an Investigator, or designated site personnel (e.g., nurse practitioners, physician assistants, research fellows) listed on the Delegation of Authority Log.

The physical examination will be a review of the major organ systems including general appearance, HEENT, lymphatic, respiratory, cardiovascular, chest, abdomen, gastrointestinal, and musculoskeletal.

Clinically significant findings prior to investigational product administration are to be captured as medical history.

Clinically significant findings after the start of investigational product administration are captured and reported as AEs, if they meet the definition of an AE per Section 10.2.1.

#### 10.1.4. Immunologic Assessments

Serum for DSA testing will be collected following standard institutional procedures for blood collection and submitted to a central laboratory for analysis. Instructions on collection, processing and shipping the samples to the central laboratory are in the Laboratory Manual.

Elevation of HLA antibodies against the donor cells (i.e., DSAs) to determine a level considered clinically significant using mean florescence intensity [MFI]

#### 10.1.5. Clinical Laboratory Assessments

All blood samples are to be collected following the standard institutional procedures for blood collection and submitted to a central laboratory for analysis. If central labs cannot be used, local labs can be used upon receipt of sponsor approval. Instructions on collection, processing, storage and shipping the samples to the central, or local if applicable, laboratory are in the Laboratory Manual.

#### 10.1.6. Hematology

Hematological testing will include complete blood count (CBC) with white blood cell (WBC) differential, hemoglobin, hematocrit, and platelet count.

#### 10.1.7. Serum Chemistry

Serum chemistry testing will include the following: basic metabolic panel (glucose, sodium, potassium, chloride, bicarbonate, blood urea nitrogen [BUN], creatinine, calcium), comprehensive hepatic panel (albumin, alkaline phosphatase, total protein, alanine aminotransferase [ALT], aspartate aminotransferase [AST], gamma-glutamyl transferase (GGT), direct bilirubin, total bilirubin), and creatine kinase.

#### 10.1.8. Coagulation Panel

Blood for a coagulation panel consisting of D-dimer, fibrinogen, PT/aPTT, INR, CRP, and ESR will be collected and analyzed locally at Months 48, 51, 54, and 57. During each visit, blood for the coagulation panel will be drawn pre-dose, 2-hours ( $\pm$  30 minutes) post dose, and 24 hours ( $\pm$  12 hours) post dose.

## 10.2. Adverse and Serious Adverse Events

#### 10.2.1. Definition of Adverse Events

#### 10.2.1.1. Adverse Event (AE)

An AE is any untoward medical occurrence associated with the use of a drug in humans, whether or not considered drug related. It may be indicated by physical sign, symptom, clinically significant laboratory abnormalities, and/or disease temporally associated with a medical (investigational) treatment, procedure, or product, whether or not related to the medical (investigational treatment, procedure or product. This definition includes intercurrent illnesses or injuries, exacerbation of pre-existing conditions, or events occurring due to abuse or overdose.

Any condition that was pre-existing is not an adverse event unless there is a change in the nature, severity, or degree of the condition.

Clinical laboratory abnormalities are considered AEs when deemed clinically significant by the Investigator and/or lead to a change in the subject's functional status.

An AE does not include:

- Medical or surgical procedures (e.g., colonoscopy, biopsy). The medical condition that leads to the procedure is an AE.
- Social or convenience hospital admissions where an untoward medical occurrence did not occur.
- Day-to-day fluctuations of pre-existing disease or conditions present or detected at the start of the trial that do not worsen.
- The disease/disorder being studied or expected progression, signs, or symptoms of the disease/disorder being studied unless more severe than expected for the subject's condition.

All Investigators conducting investigative studies supported by Capricor must report both expected and unexpected SAEs to Capricor, or designee, and their individual Institutional Review Board (IRB) in compliance with their institutional policies. Please see Section 10.2.4 or further details on event reporting.

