DMD symptoms begin in early childhood, with degeneration occurring progressively in the skeletal musculature and ultimately in the heart and respiratory muscles, resulting in premature death (Hendriksen et al., 2015). Progressive weakness and muscle atrophy caused by degenerating muscle fibers begins in the lower extremities and pelvis before spreading into the upper extremities. Other symptoms include loss of some reflexes, a waddling gait, frequent falls, difficulty when rising from a sitting or lying position or when climbing stairs, changes to overall posture, and impaired breathing. Many children precipitously lose the ability to run or jump. The atrophied muscles, in particular the calf muscles, and less commonly, muscles in the buttocks, shoulders, and arms, may be enlarged by an accumulation of fat and connective tissue, causing them to look larger and healthier than they actually are ("pseudohypertrophy"). Bone thinning and scoliosis are common. Ultimately, a wheelchair becomes necessary, in most cases between 12 to15 years of age (Henricson et al., 2013).

As the disease progresses, the muscles in the diaphragm that assist in breathing and coughing become weaker. Affected individuals experience breathing difficulties, respiratory infections, and swallowing problems. Almost all DMD patients will develop cardiomyopathy (Aartsma-Rus et al., 2016). Pneumonia, compounded by cardiac involvement, is the most frequent cause of death, which typically occurs in the late teens or early 20s. However, improvements in multidisciplinary care, in particular respiratory care and various forms of assisted ventilation, have extended the life expectancy; numerous individuals with DMD now survive into their 30s, and some even into their 40s (Emery, 2002; Bushby et al., 2010; Bushby et al., 2010).

No pharmacologic or biological therapies proven to stop or reverse the progression of DMD have been approved in the US. Disease management consists primarily of preventive measures as well as active interventions to address the primary and secondary aspects of the disorder.

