# 6.5. Dose Adjustment Criteria

There are no planned dose adjustments. Should an acute toxicity arise during the infusion (e.g., hypersensitivity reaction, pulmonary decompensation, etc.), the infusion should be terminated immediately, and the actual total dose administered recorded. Any decision about re-challenging in a subsequent infusion should be made after discussions with the Investigator, Medical Monitor, Data Safety Monitoring Board (DSMB), and other medical experts that may be required to make an informed decision.

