#### 10.2.1.2. Serious Adverse Event (SAE)

An AE is considered "serious" if, in the view of either the Investigator or Capricor, it results in any of the following outcomes:

- Death
- Life-threatening adverse event
- Inpatient hospitalization or prolongation of existing hospitalization
- Persistent or significant incapacity or substantial disruption of the ability to conduct normal life functions
- Congenital anomaly/birth defect

Important medical events that may not result in death, be life-threatening, or require hospitalization may be considered serious when, based upon appropriate medical judgment, they may jeopardize the subject and may require medical or surgical intervention to prevent one of the outcomes listed in this definition.

Examples of such medical events include bronchospasm requiring intensive treatment in an emergency room or at home, blood dyscrasias, or convulsions that do not result in inpatient hospitalization, or the development of drug dependency or drug abuse.

Complications that occur during a hospitalization are AEs. When the hospitalization is prolonged due to the complication or the complication fulfills any other serious criteria, the event is reported as an SAE. Hospitalization for elective treatment of a pre-existing condition that did not worsen from baseline is not considered an SAE.

Page 48 of 78 Capricor, Inc. - Company Confidential

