### 7.1 Adverse Events

AEs will be coded using MedDRA coding system (Version 23.1).

The following AEs are defined as TEAEs:

- AEs that occur after the initiation of the IV catheter placement for the initial dose of IP
- AEs with a completely missing start date, or similarly, AEs that start the same month and year as IP administration but that have a missing start day.

TEAEs are considered to be related to IP/administration procedure if the relationship of the particular event is marked as "possible" or "probable".

Subject listings of all AEs as reported will be provided. Serious AEs and TEAEs that are assessed as related to the IP or administration procedure, and hypersensitivity reactions/acute respiratory decompensation will be listed separately.

All summary tables will be reported using TEAEs. Additionally, TEAEs by maximum severity and TEAEs that are related to the IP or administration procedure and hypersensitivity reactions/acute respiratory decompensation will be summarized.

TEAEs will be displayed by MedDRA SOC and PT, with subjects who experience the same TEAE counted only once for that event and subjects who have more than one TEAE within a SOC counted only once in that SOC. The numbers and percentages of subjects with an event, as well as the number of events that were reported, will be calculated.

The summary tables will be prepared first for 12 months from the date of first IP administration during the OLE Phase and then again through 60 months in the OLE Phase.

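### The adverse event definition excludes expected DMD progression with no override for serious outcomes, and does not say whether this or its own rule on exacerbations prevails

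*Protocol*

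**What the plan says.** Protocol 10.2.1.1 defines an AE broadly and then lists what an AE does not include. One item on that list reads: "The disease/disorder being studied or expected progression, signs, or symptoms of the disease/disorder being studied unless more severe than expected for the subject's condition".

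The same section also has text that points the other way. Of the AE definition it says: "This definition includes intercurrent illnesses or injuries, exacerbation of pre-existing conditions, or events occurring due to abuse or overdose". It adds that a pre-existing condition becomes an AE once its nature, severity or degree changes. No sentence ranks these statements against the exclusion.

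Protocol 10.2.1.2 takes an AE as its starting point and calls it serious "if, in the view of either the Investigator or Capricor, it results in any of the following outcomes"; the list that follows includes death, life-threatening events and inpatient hospitalisation. Protocol 10.2.4 then attaches the reporting duties to those classes: AEs go into the database, SAEs go to the sponsor within 24 hours, and SAEs go to the DSMB at least twice a year.

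Both safety endpoints (Protocol 6.2.1 and 6.2.2) are the incidence and severity of treatment-emergent AEs (TEAEs), through Month 12 and Month 60. SAP 7.1 builds all its summary tables from TEAEs.

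**The concern.** The exclusion is applied before anything is recorded, by an investigator who knows that every subject is on deramiocel. Its one exception asks whether the event is worse than would be expected for that subject. It does not ask what the event led to. An event that ends in admission or death can therefore meet a seriousness criterion and still be kept out of the AE record, if the site regards it as the course the disease was going to take.

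In this disease that judgement falls on the most important events. Protocol 4.1 describes breathing difficulty, respiratory infection and near-universal cardiomyopathy as features of DMD, and says: "Pneumonia, compounded by cardiac involvement, is the most frequent cause of death, which typically occurs in the late teens or early 20s". The trial follows subjects for about 60 months with no concurrent control arm. Two sites could record the same admission differently and both point to 10.2.1.1. If serious events are left out in this way, the reported TEAE and SAE frequencies are too low, and no analysis in the SAP would show it.

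**Working it through.** The plan gives no figure to reproduce here. The check follows one type of event through the text.

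**Event traced:** an unplanned admission for respiratory failure, between two infusions, in a subject with advanced disease.

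1. *Is it an AE?* Under the exclusion in 10.2.1.1, no, if the investigator judges it expected for this subject. Under the exacerbation and change-in-severity sentences of the same section, yes. The text does not settle which applies.
2. *Does the outcome settle it?* No. The exclusion does not mention outcomes. The admission exceptions in 10.2.1.1 (social or convenience stays) and 10.2.1.2 (elective treatment of a condition that has not worsened) do not cover this event, but neither do they bring it in.
3. *Can it become an SAE?* Only if step 1 gives yes, because 10.2.1.2 classifies AEs.
4. *Does another route collect it?* Section 10.2.4 sets duties for AEs, SAEs and suspected unexpected serious reactions, and has no separate rule for deaths or admissions. Section 10.1.3 uses the same filter: significant examination findings after dosing are recorded as AEs if they meet the definition in 10.2.1.
5. *Would monitoring find it?* Section 15.2 gives a minimum list of items that monitors verify for every subject. Mortalities and serious AEs are on it; hospitalisations as such are not. A death would probably become known, though that alone does not make it an SAE. An admission that was never entered as an AE has no equivalent check.

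**Result:** where step 1 is answered no, the event is missing from the TEAE tables, the 24-hour route and the SAE report to the DSMB.

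**Scale.** Inputs: 13 subjects in the extension (SAP 3.1 and 4.1); a ceiling of 16 (Protocol 6.3 and 13.2). For one subject whose only serious event is omitted, the change in the proportion with any SAE is 1/n:

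- n = 13: 1/13 = 0.077, or 7.7 percentage points
- n = 16: 1/16 = 0.063, or 6.3 percentage points

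If that subject has another SAE on record, the subject-level proportion does not change and only the event count falls. SAP 7.1 lists SAEs and does not name a separate SAE incidence table, so this proportion is one that a reader would form from the listing.

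**The case against.** The strongest reply is that 10.2.1.1, read as a whole, favours capture. The exclusion is judged against the individual subject's condition. Intercurrent illness and worsening of a pre-existing condition count as AEs, and pneumonia fits readily under either. Section 10.2.1.2 treats complications during a hospital stay as AEs. Protocol 7.2 excludes subjects at near-term risk of respiratory decompensation, so early in the trial such an event would be hard to call expected. This largely stands. It means that the text is ambiguous and does not bar reporting outright, and that the defect is the lack of a ranking rule. The entry screen also gives less assurance as 60 months pass.

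Four stronger readings are tempting, and the documents do not support them.

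- *That the protocol contradicts itself over one event.* Protocol 6.5 gives as examples of acute toxicity "hypersensitivity reaction, pulmonary decompensation, etc", but only for events during the infusion, which nobody would plausibly call expected progression. In SAP 7.1, "hypersensitivity reactions/acute respiratory decompensation will be listed separately" pairs respiratory decompensation with hypersensitivity. A slow decline is a different event. Protocol 10.2.1.3, on expected AEs, does not list respiratory decompensation, so it cannot be called a named product toxicity beyond infusion-time events.
- *That the SAE record is the only way to notice a faster decline.* PUL 2.0, vital signs and physical examination are done at every visit from Day 1, cardiac MRI is planned from Month 24, and the DSMB reviews efficacy as well as safety (Protocol 14.1).
- *That omitted events are lost for good.* With 13 subjects, sites can be asked.
- *That a number of lost events can be given.* Multiplying 13 subjects by 5 years gives at most 65 subject-years. The documents give neither an event rate nor the share of events that sites would exclude.

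**Conclusion.** The point holds as a gap in the definition. Section 10.2.1.1 lets a serious cardiac or respiratory event be left out of the AE record on a judgement that it was expected, conflicts with its own sentences on exacerbation and worsening, and does not say which governs. Unplanned admissions between infusions are the most exposed; deaths are partly protected by monitoring.

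No passage shows that any event was omitted. Any downward bias in the safety endpoints depends on how sites read the section, and its size is unknown. The figure of 7.7 percentage points shows how much one subject weighs when n = 13, and is not an estimate of bias. It assumes that the omitted event is that subject's only serious one. The case for acting is that the repair is cheap and the trial is small, open-label and single-arm.

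**What to change.** Four changes, all to recording and none to treatment:

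1. Add to the progression item in Protocol 10.2.1.1 that any event meeting a seriousness criterion in 10.2.1.2 is recorded as an AE and as an SAE, whether or not it is attributed to DMD progression. The exception for elective admissions in 10.2.1.2 stays.
2. State that this sentence prevails over the other sentences of 10.2.1.1, so that the exclusion and the exacerbation rule no longer compete.
3. Add a case report form field for attribution to DMD progression, and have SAP 7.1 show the TEAE tables and SAE listing with and without the events so attributed.
4. Query each site once for deaths and unplanned admissions since first infusion that were not entered, and record those found under the new rule.

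The cost is one protocol edit, one form field, a short SAP addition and a single query covering 13 subjects. The downside is a few more SAE forms and a less favourable SAE count. Showing results with and without progression-attributed events lets a reader judge that count fairly.
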